9.9. Definition of end of trial

The end of the trial is the date of the last assay conducted on the last sample collected.

10. TRIAL INTERVENTIONS

See APPENDIX A: SCHEDULE OF PROCEDURES for details

10.1. Investigational Medical Product(s) (IMP) Description

Table 2: The marketing authorisation and IMP labelling status of the vaccines:

Vaccine	UK Marketing authorisation status	IMP labelling status
Pfizer/BioNTech BNT162b2	Approved for use under a temporary authorisation of the supply of an unlicensed vaccine; regulation 174 of the Human Medicines Regulations 2012.	Not IMP labelled, product will be used as supplied by manufacturer for national supply
Novavax SARS-CoV-2 rS/Matrix-M1 Adjuvant NVXCoV2373	No marketing authority or emergency use approval currently	IMP labelling required

10.1.1. VACCINE A – Pfizer BioNTech (BNT162b2)

BNT162b2 is a lipid nanoparticle-formulated, nucleoside-modified mRNA vaccine that encodes trimerised SARS-CoV-2 spike glycoprotein. BNT162b2 encodes the SARS-CoV-2 full-length spike, modified by two proline mutations to lock it in the prefusion conformation and more closely mimic the intact virus with which the elicited virus-neutralizing antibodies must interact. mRNA vaccines use the pathogen's genetic code as the vaccine; this then exploits the host cells to translate the code and then make the target spike protein. The protein then acts as an intracellular antigen to stimulate the immune response. The mRNA is then degraded within days. The vaccine RNA is formulated in lipid nanoparticles (LNPs) for more efficient delivery into cells after intramuscular injection.

10.1.1.1. Dosage, scheduling and packaging

The dose of Pfizer BioNTech COVID-19 vaccine is 30µg contained in 0.3ml of the diluted vaccine. Each pack of the Pfizer BioNTech vaccine contains 195 vials with 6 full doses per vial (975 doses per pack). It is supplied with 0.9% sodium chloride diluent for injection plastic ampoules. Participants randomised to the one third dose BNT162b2 vaccine group will receive a 0.10 ml dose.

10.1.2. VACCINE B – Novavax, NVXCoV2373

Novavax, NVXCoV2373 is a nano-particle vaccine. It is constructed from the full-length wild-type (prototype Wuhan sequence) pre-fusion trimers of SARS-CoV2 spike glycoprotein. The native protein has been modified with several substitutions to limit protease cleavage and enhance thermal stability (the putative native furin cleavage site has been modified from RRAR to QQAQ and 2 proline substitutions (positions K986P and V987P) in the HR1 domain). It has also been optimised for expression in insect (*Spodoptera frugiperda*) Sf9 cells. The recombinant S-protein genes are cloned into a baculovirus vector before being transferred into Sf9 cells. These cells then produce the protein which is extracted and purified. It is co-formulated with a saponin-based adjuvant, Matrix-M1™.

10.1.2.1. Dosage, scheduling and packaging

The dose of NVXCoV2373 is 5 µg recombinant spike protein with 50 µg Matrix-M1 adjuvant (0.5ml). The vaccine is supplied in 10 full dose vials.

10.2. Blinding of IMPs

See Section 9.5 for details.

10.3. Storage of IMP

Vaccines will be stored in accordance with manufacturers' recommendations.

All movements of the study vaccines will be documented in accordance with existing standard operating procedure (SOP). Vaccine accountability, storage, shipment and handling will be in accordance with relevant SOPs and forms. To allow for participants to receive the vaccine in a short time period, multiple clinic locations may be used. In this instance vaccines will be transported in accordance with local SOP's and approvals as required.

10.3.1. Vaccine A - Pfizer BioNTech (BNT162b2)

The Pfizer BioNTech vaccine should be stored at -70°C +/- 10°C and has shelf life of 6 months. Once thawed, the vaccine may be stored for one month (for the purposes of this study, this is

considered to be 30 days) at 2 to 8°C. It should be used as soon as practically possible and within 6 hours of dilution.

10.3.2. Vaccine B – Novavax, NVXCoV2373

SARS-CoV-2 rS and Matrix-M1 adjuvant should be stored at 2°C to 8°C and not frozen.

10.4. Compliance with trial treatment

All vaccinations will be administered by the research team and recorded in the CRF. The study medication will be at no time in the possession of the participant and compliance will not, therefore, be an issue.

10.5. Accountability of the trial treatment

Accountability of the IMPs will be conducted in accordance with the relevant SOPs.

10.6. Concomitant medication

As set out by the exclusion criteria, volunteers may not enter the study if they have received any vaccine within 7 days before enrolment (which is defined as occurring at the time of receipt of the first study vaccine), or intend to receive within 7 days after the COVID-19 vaccine, and the subsequent COVID-19 immunisation should be scheduled to given at least 7 days before or after any non-study vaccine. Volunteers may not enter the study if they have participated in another research trial involving an investigational product in the previous 12 weeks, or if they have used immunosuppressant medication within 6 months prior to enrolment or if receipt is planned at any time during the study period (except topical steroids and short course of low dose steroids < 14 days). Concomitant medications taken at enrolment will be recorded, as will new medications within the 28 days after each immunisation.

10.7. Post-trial treatment

Decisions regarding the need for a boost dose in any of the heterologous prime/boost schedules, the nature of any boost dose and mode of delivery (e.g. NHS vs study site) will be made in consultation with the DSMB and trial steering committee.

10.8. Other treatments (non-IMPs)

Participants will be advised that they may take paracetamol prophylactically after vaccine administration. This will be from the participants own supplies rather than supplied by the study team.

10.9. Other interventions

There are no additional interventions other than those specified in this protocol.

11. SAFETY REPORTING

11.1. Safety reporting window

Safety reporting for the trial will commence once the first participant is consented; and will end 10 months after the last participant has received the second dose of an IMP for SAEs and Adverse Events of Special Interest (AESIs).

For individual participants the reporting period begins when they are consented, in person at the V1, and ends 12 months after the first dose of vaccine for SAEs and AESIs.

All adverse events (AEs) that result in a participant's withdrawal from the study will be followed up until a satisfactory resolution occurs, or until a non-study related causality is assigned (if the participant consents to this).

11.2. Adverse Event Definitions

Adverse Event (AE)	Any untoward medical occurrence in a participant to whom a medicinal product has been administered, including occurrences which are not necessarily caused by or related to that product.
Adverse Reaction (AR)	An untoward and unintended response in a participant to an investigational medicinal product which is related to any dose administered to that participant. The phrase "response to an investigational medicinal product" means that a causal relationship between a trial medication and an AE is at least a reasonable possibility, i.e. the relationship cannot be ruled out. All cases judged by either the reporting medically qualified professional or the Sponsor as having a reasonable suspected causal relationship to the trial medication qualify as adverse reactions.
Adverse Events of Special Interest (AESI)	Adverse events identified as being of particular relevance to the IMP's. These will also be reported as an SAE, if meeting SAE criteria (e.g. hospitalisation)
Serious Adverse Event (SAE)	A serious adverse event is any untoward medical occurrence that: 
 - Results in death - Is life-threatening - Requires inpatient hospitalisation or prolongation of existing hospitalisation - Results in persistent or significant disability/incapacity - Consists of a congenital anomaly or birth defect

	
Other ‘important medical events’ may also be considered a serious adverse event when, based upon appropriate medical judgement, the event may jeopardise the participant and may require medical or surgical intervention to prevent one of the outcomes listed above.
 
NOTE: The term "life-threatening" in the definition of "serious" refers to an event in which the participant was at risk of death at the time of the event; it does not refer to an event which hypothetically might have caused death if it were more severe.

Serious Adverse Reaction (SAR)	An adverse event that is both serious and, in the opinion of the reporting Investigator, believed with reasonable probability to be due to one of the trial treatments, based on the information provided.
Suspected Unexpected Serious Adverse Reaction (SUSAR)	
A serious adverse reaction, the nature and severity of which is not consistent with the Reference Safety Information for the medicinal product in question set out:
 
 1. In the case of a product with a marketing authorisation, in the approved summary of product characteristics (SmPC) for that product 2. In the case of any other investigational medicinal product, in the approved investigator’s brochure (IB) relating to the trial in question

NB: to avoid confusion or misunderstanding of the difference between the terms “serious” and “severe”, the following note of clarification is provided: “Severe” is often used to describe intensity of a specific event, which may be of relatively minor medical significance. “Seriousness” is the regulatory definition supplied above.

11.3. Assessment results outside of normal parameters as AEs and SAEs

11.3.1. Clinical

Abnormal clinical findings from medical history or examination will be assessed as to their clinical significance throughout the trial. If an abnormal finding is deemed to be clinically significant, the participant will be informed and appropriate medical care arranged with the permission of the participant as per Section 9.5.

11.4. Assessment of severity

The severity of clinical adverse events will be assessed according to scales listed in the Clinical Study Plan and in Tables 3 and 4 below.

Table 3: Severity grading for local adverse events

Adverse Event	Grade	Intensity
Pain at injection site	1	Pain that is easily tolerated
	2	Pain that interferes with daily activity
	3	Pain that prevents daily activity
	4	A&E visit or hospitalization
Tenderness	1	Mild discomfort to touch
	2	Discomfort with movement
	3	Significant discomfort at rest
	4	A&E visit or hospitalization
Erythema at injection site*	1	2.5 - 5 cm
	2	5.1 - 10 cm
	3	>10 cm
	4	Necrosis or exfoliative dermatitis
Induration/Swelling at injection site	1	2.5 – 5 cm and does not interfere with activity
	2	5.1 - 10 cm or interferes with activity
	3	>10 cm or prevents daily activity
	4	Necrosis
*erythema \leq2.5cm is an expected consequence of skin puncture and will therefore not be considered an adverse event		

Table 4: Severity grading for local and systemic AEs

GRADE 0	None
GRADE 1	Mild: Transient or mild discomfort (< 48 hours); No interference with activity; No medical intervention/therapy required
GRADE 2	Moderate: Mild to moderate limitation in activity – some assistance may be needed; no or minimal medical intervention/therapy required

GRADE 3	Severe: Marked limitation in activity, some assistance usually required; medical intervention/therapy required.
GRADE 4	Potentially Life-threatening: Requires assessment in A&E or hospitalisation

11.5. Assessment of causality

For every recorded AE, an assessment of the relationship of the event to the administration of the vaccine will be undertaken by the CI-delegated clinician. An interpretation of the causal relationship of the intervention to the AE in question will be made, based on the type of event; the relationship of the event to the time of vaccine administration; and the known biology of the vaccine therapy. Alternative causes of the AE, such as the natural history of pre-existing medical conditions, concomitant therapy, other risk factors and the temporal relationship of the event to vaccination will be considered and investigated. Causality of SAEs will be assigned by the reporting investigator at the time of reporting, as described in SOP OVC005 Safety Reporting for CTIMPs. For all other AE's causality assessment will take place during planned safety reviews, interim analyses (including if the study is paused by the DSMB due to safety concerns) and at the final safety analysis. Causality assessment will be recorded on the eCRF.

Table 1: Guidelines for assessing the relationship of vaccine administration to an AE.

0	No relationship	No temporal relationship to study product and Alternate aetiology (clinical state, environmental or other interventions); and Does not follow known pattern of response to study product
1	Unlikely	Unlikely temporal relationship to study product and Alternate aetiology likely (clinical state, environmental or other interventions) and Does not follow known typical or plausible pattern of response to study product.
2	Possible	Reasonable temporal relationship to study product; or Event not readily produced by clinical state, environmental or other interventions; or Similar pattern of response to that seen with other vaccines
3	Probable	Reasonable temporal relationship to study product; and Event not readily produced by clinical state, environment, or other interventions or Known pattern of response seen with other vaccines
4	Definite	Reasonable temporal relationship to study product; and

Event not readily produced by clinical state, environment, or other interventions; **and**
Known pattern of response seen with other vaccines

11.6. Procedures for reporting Adverse Events

11.6.1. Solicited AEs

Participants will be asked to record local and systemic AEs for 7 days (and longer if symptoms persist at day seven, until resolution or stabilisation) following vaccination in the electronic/paper diary (solicited AEs).

11.6.2. Unsolicited AEs

All local and systemic AEs occurring in the 28 days following each vaccination observed by the Investigator or reported by the participant, whether or not attributed to study medication, will be recorded in electronic/paper diaries or study database. All AEs that result in a participant's withdrawal from the study will be followed up until a satisfactory resolution occurs, or until a non-study related causality is assigned (if the participant consents to this) as per Section 9.8.

SAEs and AESIs will be actively solicited at each study visit throughout the entire trial period.

11.7. Reporting procedures for Serious Adverse Events

In order to comply with current regulations on SAE reporting to regulatory authorities, the event will be documented accurately and notification deadlines respected. SAEs will be reported to members of the study team immediately the Investigators become aware of their occurrence, as described in the clinical study plan. Copies of all reports will be forwarded for review to the Chief Investigator (as the Sponsor's representative) within 24 hours of the Investigator being aware of the suspected SAE. The DSMB will be notified of SAEs that are deemed possibly, probably or definitely related to study interventions; the chair of DSMB will be notified immediately (within 24 hours) of the sponsor being aware of their occurrence. SAE/AESIs will not normally be reported immediately to the ethical committee(s) unless there is a clinically important increase in occurrence rate, an unexpected outcome, or a new event that is likely to affect safety of trial participants, at the discretion of the Chief Investigator and/or DSMB. In addition to the expedited reporting above, the Investigator shall include all SAE/AESIs in the annual Development Safety Update Report (DSUR) report provided for COM-COV, COM-COV2 and COM-COV3.

In participants who have received the NVXCoV2373 vaccine in this study, SAE's will be reported to Novavax according to the conditions and timelines outlined in the contemporaneous version of the Clinical Trial Agreement between Novavax and the University of Oxford University for conduct of this study.

11.7.1. Events exempt from immediate reporting as SAEs

Hospitalisation for a pre-existing condition, including elective procedures planned prior to study entry, which has not worsened, does not constitute a serious adverse event. A&E attendances should not routinely be reported as SAEs unless they meet the SAE definition described above.

11.8. Expectedness

11.8.1. SARs

11.8.1.1. Pfizer BioNTech (BNT162b2)

If an SAE is considered as being an SAR to BNT162b2, section 4.8 of the BNT162b2 Summary of Product Characteristics will be used as the reference safety information to determine expectedness. Potential SARs considered to be expected include:

- Anaphylaxis
- Myocarditis/pericarditis
- Lymphadenopathy
- Facial nerve palsy

11.8.1.2. Novavax, NVXCoV2373

No SARs expected

11.8.2. Foreseeable Adverse Reactions

The foreseeable ARs following vaccination are as follows:

11.8.2.1. Pfizer BioNTech (BNT162b2)

Very common	Common	Uncommon	Rare	Unknown
Headache	Injection site redness	Lymphadenopathy	Acute peripheral facial paralysis	Anaphylaxis
Arthralgia	Nausea	Insomnia		Hypersensitivity
Myalgia		Pain in extremity		Myocarditis
Injection site pain/swelling		Malaise		Pericarditis

Fatigue		Injection site pruritus		
Chills				
Pyrexia				

11.8.2.2.

Novavax, NVXCoV2373

(From the IB report of data from clinical trials)

- Reactogenicity is generally mild, and vaccinations were well tolerated.
- Following first vaccination, local reactogenicity is more frequent for NVXCoV2373 than the unadjuvanted or placebo regimens.
- Tenderness and pain were the most frequent local AEs.
- Systemic reactogenicity were individually less frequent but were observed with greater frequency in the SARS-CoV-2 rS/Matrix-M1 adjuvant groups.
- Headache, fatigue, and myalgia were the most frequent systemic AEs.
- Following second vaccination, NVXCoV2373 induced greater local and systemic reactogenicity, but the majority of reported symptoms remained at grade ≤ 1 .
- Mean duration of reactogenicity events was ≤ 2 days without appreciable change in duration with second vaccination.
- Severe reactogenicity was infrequent (2 events after Dose 1 and 8 events after Dose 2), occurring more often with second vaccination and for systemic events, with placebo subjects citing similar frequencies as those receiving SARS-CoV-2rS.

11.9. No subjects sought medical intervention or refused second vaccination because of reactogenicity

11.10. Adverse Events of Special Interest

Table 2: AESIs

Immunologic	Anaphylaxis	
Neurological	Isolated anosmia/ageusia*	Meningoencephalitis
	Guillain-Barre Syndrome	Peripheral facial nerve palsy
	Acute disseminated encephalomyelitis (ADEM)	Generalised convulsion
	Aseptic meningitis	Myelitis

Haematological	Thrombosis** Stroke Thrombocytopenia*** Eosinophilia****	Coagulation disorder (includes coagulopathy, thrombosis, thromboembolism, internal/external bleed and stroke)
Cardiac	Acute cardiovascular injury (includes myocarditis#, pericarditis#, arrhythmias, heart failure, infarction)	
Dermatological	Chilblain-like lesions Single organ cutaneous vasculitis	Erythema multiforme Alopecia
Gastrointestinal	Acute liver injury †† †	Appendicitis Cholecystitis*****
Respiratory	ARDS††	
Renal	Acute kidney injury	
Other	COVID-19 disease† PIMS-TS †† ††	SARS-CoV2 positivity on a validated test

*In the absence of COVID-19

** Excluding superficial thrombophlebitis (including line-associated)

*** G3 or above

**** This will be used as a marker of skewed Th2 responses and will be routinely monitored in participants attending the COVID-19 Pathway and follow-up visits. Only G2 and above.

***** Added as an expected AR to the IB for NVXCoV2373 in Addendum 1 dated 27 Sept 2021. A further update (Addendum 2 dated 11th January 2022) removed cholecystitis as an expected AR for NVXCoV2373. Cholecystitis is therefore not considered an expected AR, though it remains an AESI.

Brighton collaboration guideline definitions for myocarditis and pericarditis as outlined in appendix D

† In particular, any occurrence of suspected vaccine associated enhanced disease (VAED) as defined by most recent Brighton Collaboration Case Definition (22)

†† In the absence of an infective aetiology (including COVID-19)

†† † As defined in Hy's Law

†† †† The Royal College of Paediatrics and Child Health has outlined a case definition for PIMS-TS.

1. A child presenting with persistent fever, inflammation (neutrophilia, elevated CRP and lymphopaenia) and evidence of single or multi-organ dysfunction (shock, cardiac, respiratory, renal, gastrointestinal or neurological disorder) with additional features (Table 8) This may include children fulfilling full or partial criteria for Kawasaki disease.

2. Exclusion of any other microbial cause, including bacterial sepsis, staphylococcal or streptococcal shock syndromes, infections associated with myocarditis such as enterovirus (waiting for results of these investigations should not delay seeking expert advice).
3. SARS-CoV-2 PCR testing may be positive or negative

AESIs should be collected and recorded in the AE reporting form in REDCap throughout the duration of this study. These should also be reported as SAEs if they fulfil the definition criteria for SAEs. All AESIs not already reported as SAEs should be included in the reports to the DSMB.

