5.2.2. Associated with phlebotomy

Localised bruising and discomfort can occur at the site of venepuncture. Infrequently fainting may occur. These will not be documented as AEs if they occur. Blood volumes collected will adhere to EC directive 2001/20/EC for paediatric blood volume sampling which states that ‘per individual, the trial-related blood loss (including any losses in the manoeuvre) should not exceed 3 % of the total blood volume during a period of four weeks and should not exceed 1% at any single time’. Based on these calculations, we will take 16ml per sampling timepoint from participants aged 12-16 years on each visit for immunology bloods. Some participants will turn 17 during the trial and become eligible for blood donation; they will be asked to refrain from this for the duration of their trial involvement.

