23. APPENDIX A: SCHEDULE OF PROCEDURES

Study timeline	Screening	D0	D56	D14 post boost	D28 post boost	D132 post boost	D236 post boost
Study window		Within 120 days of screening	Day 56–70 post prime vaccine at D0 or Day 56 + post prime vaccination in community	Day 12-17 Post D56	Day 28-42 post D56	Day 112-152 post D56	Day 224-252 post D56
Pre - screening online consent	X*						
Informed consent	X	X					
Medical history	X	X					
Interim medical history		X	X	X	X	X	X
Physical examination (as required)	(X)	(X)	(X)	(X)	(X)	(X)	(X)
Urine test (Pregnancy) (if required)		(X)**	X				
COVID-19 vaccination		(X)**	X				

COVID-19 immunogenicity bloods		(X)**	X	X	X	X	X
Troponin and NT-proBNP blood test		(X)**	X	X	X		
Saliva and nasal fluid test (if participant consents)		(X)**	X	X			
Diary review			X	X	X		
SAE/AESI check			X	X	X	X	X

* Pre - screening online consent. Restricted to taking a limited medical history online, contacting the GP for further medical record if required and telephone screening visit(s)

**Procedures performed only if prime dose administered in the study

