25. APPENDIX C: BLOOD SAMPLING

Study timeline	D0	D56	D14 post boost	D28 post boost	D132 post boost	D236 post boost
COVID-19 vaccination	X	X				
Secondary endpoints	Anti-spike IgG* Anti-nucleocapsid IgG* ELIspot* Troponin & NT-proBNP*	Anti-spike IgG Anti-nucleocapsid IgG ELIspot Troponin & NT-proBNP	Anti-spike IgG ELIspot Troponin & NT-proBNP	Anti-spike IgG PBMC for storage Troponin & NT-proBNP	Anti-spike IgG Anti-nucleocapsid IgG ELIspot	Anti-spike IgG Anti-nucleocapsid IgG ELIspot
Total volume blood per visit	16	16	16	16	16	16
Total volume by end of study						96 ml

* Procedures performed only if prime dose administered in the study

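### Section 11.10 promises routine monitoring of eosinophilia, but no scheduled visit includes a blood count, so few or no reported cases would not show absence

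*Protocol*

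**What the plan says.** The AESI table in Protocol section 11.10 lists eosinophilia under haematological events. Its footnote makes three statements:

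- Purpose: "This will be used as a marker of skewed Th2 responses".
- Method: it "will be routinely monitored in participants attending the COVID-19 Pathway and follow-up visits".
- Threshold: "Only G2 and above".

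Section 9.6.1.2 leaves sampling at follow-up visits to the schedule in Appendix A, and section 9.7 refers to Appendix C for the frequency and volume of blood draws. Appendix A has two blood rows, "COVID-19 immunogenicity bloods" and "Troponin and NT-proBNP blood test". Appendix C itemises the assays at each visit. Section 5.2.2 gives the use of the blood: "we will take 16ml per sampling timepoint from participants aged 12-16 years on each visit for immunology bloods".

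AESIs are a secondary safety outcome collected throughout the study (section 6). Section 12.2 plans counts and percentages by group, with Fisher's exact test for comparisons between arms. Section 11.10 sends AESIs not already reported as serious adverse events to the DSMB.

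**The concern.** The footnote is a positive commitment: a laboratory quantity, measured routinely, with a graded threshold and a stated scientific purpose. Eosinophilia at a given grade can be identified only from a measured cell count, and the parts of the protocol that govern blood sampling contain none. The footnote also relies on a COVID-19 Pathway that is named nowhere else.

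What is at stake is how the AESI results are read. Anyone who takes section 11.10 at its word will treat few or no cases as the result of systematic surveillance, and any difference between arms, or lack of one, as informative. The primary outcome, the immunogenicity outcomes, the randomisation and the sample size are not affected.

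**Working it through.** **1. The statement against the schedule**

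| Where in the protocol | What it provides |
|---|---|
| 9.6.1.1.3, D0 samples | Immunogenicity bloods, cardiac markers; optional nasal fluid and saliva |
| Appendix A | Two blood rows: immunogenicity, and troponin with NT-proBNP |
| Appendix C, D0 and D56 | Anti-spike IgG, anti-nucleocapsid IgG, ELISpot, troponin and NT-proBNP |
| Appendix C, D14 post boost | Anti-spike IgG, ELISpot, troponin and NT-proBNP |
| Appendix C, D28 post boost | Anti-spike IgG, stored PBMC, troponin and NT-proBNP |
| Appendix C, D132 and D236 post boost | Anti-spike IgG, anti-nucleocapsid IgG, ELISpot |

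Full blood counts scheduled: 0 of 6 visits. (Participants primed in the community have no D0 draw, so 0 of 5 for them.)

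Appendix C's "Total volume blood per visit" is 16 ml, and its "Total volume by end of study" is 96 ml. Check: 6 × 16 = 96 ml, which agrees. The volume alone does not rule out a blood count within the 16 ml. The itemised assays and section 5.2.2 show that none is planned.

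**2. Other places where a count might be found**

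- Section 4 expands the abbreviation FBC, but the term is not used again.
- Section 9.8 mentions safety bloods after withdrawal, but none are scheduled anywhere.
- Section 7.4: after a new positive test the participant makes a diary entry and may continue. No visit or draw follows.
- Section 9.6.4: for COVID-19 admissions the team requests medical notes, which may include blood results.
- Section 11.3 has only a clinical subsection, and the tables in section 11.4 contain no laboratory grading scale.

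**3. What a zero would be worth (illustration)**

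The documents give no rate of eosinophilia and no detection probability, so both are assumed here. The arm size of 90 is the one used in section 12.1.

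If everyone were measured, the exact two-sided 95% upper limit for 0 of n is 1 − 0.025^(1/n):

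- n = 90: 1 − 0.025^(1/90) = 4.0%
- n = 270: 1 − 0.025^(1/270) = 1.4%

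If a fraction d of true cases comes to light and the true rate is p, the probability that an arm of 90 reports none is (1 − p·d)^90. For example, p = 5% and d = 5% give (1 − 0.0025)^90 = 0.798.

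| Fraction detected, d | p = 2% | p = 5% | p = 10% |
|---|---|---|---|
| 100% | 0.162 | 0.010 | <0.001 |
| 10% | 0.835 | 0.637 | 0.405 |
| 5% | 0.914 | 0.798 | 0.637 |
| 2% | 0.965 | 0.914 | 0.835 |

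With full measurement, a zero would count strongly against a rate of 5% or more. With detection of 5% or less, zero is the most likely result at all three rates. Since d is unknown, an observed zero sets no usable bound on p.

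**The case against.** The strongest reply is that this is one footnote on one of many AESIs. Th2 skewing is not an objective or a planned analysis, and section 12.2 promises neither a separate eosinophilia row nor any inference from a zero. Documents not shown might also fill part of the gap: section 11.10.1 leaves investigations of COVID-19 cases to a laboratory analysis plan, and section 11.4 refers to a Clinical Study Plan for severity scales. This limits the weight of the point but does not remove it. Section 11.10.1 concerns possible enhanced disease in COVID-19 cases, and a grading scale is not a measurement. Neither puts a count into the follow-up visits that the footnote names. Nor is this detail left to a SAP: the protocol itself sets out the blood schedule.

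Three stronger readings are tempting, and the documents do not support them.

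- A reader might infer that nothing at all is measured and that a zero is certain. Section 11.6.2 has AESIs actively sought at every visit, and section 9.6.4 obtains hospital notes. Ascertainment is near-absent and unsystematic, not nil.
- A reader might extend the point to thrombocytopenia. Its footnote sets only a reporting threshold of grade 3 and claims no routine monitoring, so there is no contradiction.
- A reader might conclude that the Th2 rationale should be struck out, or that the footnote rather than the schedule is the error. The documents do not show the rationale to be wrong, and they do not show which passage reflects the sponsor's intention.

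**Conclusion.** The point holds as an internal contradiction. Section 11.10 states a safety-monitoring property that the schedule does not have: no blood count at any of the six blood visits, and no Pathway described. Few or no reported cases of eosinophilia would therefore not be evidence of absence.

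The contradiction rests on the text alone. The probabilities only show scale and depend on the assumed rates, the assumed detection fractions and 90 participants per arm. The correction is worth making because AESIs are tabulated by arm and reported to the DSMB. It does not threaten the trial's main results.

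**What to change.** Reconcile the eosinophilia footnote in section 11.10 with Appendices A and C, so that the stated monitoring and the scheduled procedures agree. Which of the two reflects the intended design is for the sponsor to settle.

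If no count is scheduled, remove the statements about routine monitoring and the COVID-19 Pathway. Say that eosinophilia is recorded only when it comes to light through AESI questioning or medical records. In the by-arm AESI tables and the DSMB reports, label it as not systematically measured rather than as zero incidence.

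That route costs wording only, and the described surveillance becomes somewhat more modest. If the sponsor instead keeps the monitoring statement, the schedule, the meaning of the Pathway and the grading scale would all have to be set out to match. That is a larger amendment, whose cost the documents do not allow one to estimate.
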